6.1.3.5 Categorical analysis of Hb values

The following endpoints will be analyzed : proportion of Hb values within 10.0-12.0 g/dL and ≥ 10.0 g/dL, by time intervals, the percentage of time with Hb values falling in each Hb interval (< 10.0 g/dL, within 10.0-12.0 g/dL, ≥ 10.0 g/dL, > 12.0 g/dL, > 13.0 g/dL and > 14.0 g/dL) during the Efficacy Emergent Period and the potential Excessive Hematopoiesis (EH).

Proportion of Hb values :

The following proportion in percentage for each subject will be defined:

- Number of Hb values within 10.0-12.0 g/dL / Total number of Hb values*100 and (≥ 10.0 g/dL)/Total number of Hb values*100

in weeks 28 to 36, 44 to 52 and 96 to 104 without use of rescue therapy within 6 weeks prior to and during this 8 week evaluation period. All scheduled and unscheduled hemoglobin values that belong to each period will be taken into account using the analysis windows defined in [Table 31](#), Section [7.11.4](#)

Percentage of time :

The percentage of time each patient has a Hb value <10.0 g/dL, within 10.0-12.0 g/dL, ≥ 10.0 g/dL, > 12.0 g/dL, > 13.0 g/dL or > 14.0 g/dL

will be calculated (as a percentage of the total of the length of time between the first and last Hb assessment during the evaluated period). The percentage of time will be calculated via linear interpolation. That is, if the change in Hb category (for instance from within 10.0-12.0 g/dL to > 12.0 g/dL) occurs between two visits V0 and V1, the day of change will be calculated by:

[figure not shown]
$$x = x_0 + (y - y_0) \frac{(x_1 - x_0)}{(y_1 - y_0)}$$

Where x_1 and x_0 are the dates when Hb was measured at V0 and V1 respectively, y_0 and y_1 are the Hb value at the respective visits V0 and V1 and y is the level of the Hb

boundary (i.e 12.0, 13.0 or 14.0 g/dL). Percentage of time each subject has Hb value ≥ 10.0 g/dL will be derived as 100% - percentage time for Hb values < 10 g/dL.

Figure 1 shows visually how the linear interpolation will calculate the total number of days that a subject is in each Hb category for an example subject:

Figure 1 Example of Linear Extrapolation

In case that several Hb values are on the same day the average of these values will be used to represent the Hb of that day in the above formula. This calculation will provide the day that the change in Hb value occurs. The number of days that the Hb value has been in each category will be determined and the percentage calculated based on the length of time between the first and last Hb assessment during the evaluated period, i.e.:

Date of Last Hb assessment during the evaluated period – Date of first assessment during the evaluated period.

No imputation will be performed if no Hb value is available in relevant time windows.

In case a subject requires rescue therapy within 6 weeks prior to and during these 8-week evaluation periods, refer to Section 7.11.1 for imputation rules.

Potential Excessive Hematopoiesis (EH), regardless use of rescue therapy, based on Hb central lab will be defined as:

- Hb increase by >2.0 g/dL between any two visits within 4 weeks of treatment during the Efficacy Emergent Period.

Time to first occurrence of potential EH regardless the use of rescue therapy during the Efficacy Emergent Period will be defined in weeks as :

$$(\text{First event date} - \text{Analysis date of first dose intake} + 1) / 7$$

where 'First event date' is defined as first date of occurrence of the criterion met during the Efficacy Emergent Period.

For a subject without potential EH, the time to censoring will be calculated (in weeks) as:

$$\frac{(\text{Date of last hemoglobin assessment during the Efficacy Emergent Period} - \text{Analysis date of first dose intake} + 1)}{7}$$

Refer to Section [6.1](#) and [7.11.6](#) for the definition of the Efficacy Emergent Period.

6.1.3.6 Occurrence (number) of hospitalizations, number of days of hospitalization per patient- exposure -year and time to first hospitalization

The occurrence and the number of hospitalizations per subject during the Efficacy Emergent Period will be calculated.

The number of days of hospitalization per patient- exposure-year (PEY) will be calculated as :

$$\frac{[\text{Sum of the durations of all hospitalizations in days (Minimum ((Date of discharge, End of Efficacy Emergent Period) - Date of admission} + 1)] / [(\text{Duration of Efficacy Emergent Period in days} / 365.25)]}{}$$

When hospitalization is ongoing, the date of end of the Efficacy Emergent Period will be used for the derivation of the hospitalization duration. In case of missing dates the hospitalization duration will be imputed by the average duration per stay derived from the subjects with non-missing duration within the same treatment group . Duration of treatment exposure is defined in Section [6.5.4](#)

If the date of admission of a hospitalization record is the same as the date of discharge of the previous record, for example because two records are created to illustrate that the subject is moved from one hospital to another hospital or from a standard care to the intensive care unit (ICU), then the date of the transfer should not be counted twice and thus the hospitalizations duration for the later period is calculated as (Date of discharge – Date of admission). In such case hospitalization occurrence will also be counted only once.

Hospitalizations will also be described by reason for admission (admission for anemia or other reasons).

Time to first hospitalization in years will be defined in years as :

$$\frac{(\text{First event date during the Efficacy Emergent Period} - \text{Analysis date of first dose intake} + 1)}{365.25}$$

With 'First event date' defined as 'Date of first Admission' and 'Analysis date of first dose intake defined in Section [6.5.4](#)

For a subject without hospitalization, the time to censoring will be calculated as:

$$\frac{(\text{Date of End of Efficacy Emergent Period} - \text{Analysis date of first dose intake} + 1)}{365.25}$$

With date of End of Efficacy Emergent Period is defined in Section [7.11.6](#)

6.1.3.7 Occurrence and time to first use of rescue therapy [composite of RBC transfusions, IV iron supplementation and ESA treatment] during the first 24 weeks

Rescue medication is defined in Section [6.1.2.3](#). Start of rescue medication is only counted as event if it was started within the first 24 weeks of treatment. Subjects without event were censored at the date of the Week 24 visit.

6.1.3.8 Occurrence and time to first use of RBC transfusions, number of RBC packs per month, volume of RBC transfused per month

The blood transfusion form of the eCRF in the cumulative visit will be used to derive the number of RBC packs.

Monthly volume of blood transfused and the monthly total number of RBC units/packs (for each subject, the sum of blood volume and units transfused during the Efficacy Emergent Period / divided total number of days multiplied by 28 days) will be derived.

For RBC transfusions, when the number of units is not given but the volume transfused is given, the number of units will be estimated by volume transfused/250 mL (for transfusion of packed cell units) or volume transfused/500 mL (for transfusion of full blood).

When transfused volume is not given but the number of RBC units is given, the volume will be estimated as number of RBC units times 250 mL (for transfusion of packed cell units) or number of units times 500 mL (for transfusion of full blood).'

For subjects with use of RBC transfusion, the time to use of RBC transfusion is calculated as:

$$(\text{First event date} - \text{Analysis date of first dose intake} + 1) / 365.25$$

With 'First event date' defined as 'Date of first RBC transfusion' during the Efficacy Emergent Period and 'Analysis Date of first dose intake' defined in Section [6.5.4](#)

For a subject without use of RBC transfusion, the time to censoring is calculated as:

$$(\text{Date of End of Efficacy Emergent Period} - \text{Analysis date of first dose intake} + 1) / 365.25$$

With date of End of Efficacy Emergent Period defined in Section [7.11.6](#)

6.1.3.9 Occurrence and time to first use of IV iron supplementation. Mean monthly IV iron (mg) per subject during day 1 to week 36, weeks 37-52 and weeks 53-104 (monthly defined as a period of 4 weeks)

The use of IV iron is collected in the *Concomitant Medication* form of the eCRF. The route of administration (Intravenous) is also captured in the eCRF. All medications are coded with WHO-DD. Records selected will be those coded as IRON PREPARATIONS, ATC 3rd level code: B03A and where route is INTRAVENOUS.

Having received IV Iron is a binary variable (Yes/No), where "Yes" is defined as having at least one record selected during the Efficacy Emergent Period. The Efficacy Emergent Period will be divided in periods of 28 days and for each of these periods, the monthly mean of IV iron will be calculated.

Only use of IV Iron that was ongoing or started during the Efficacy Emergent Period will be taken into account.

The Mean Monthly IV iron use per subject (in mg) during the first 36 weeks is defined by the following formula:

$$\frac{\text{Total of IV iron use (mg) from Analysis date of first dose intake to Min(Analysis Date of Week 36 visit, Analysis date of last dose)}}{((\text{Min(Analysis Date of Week 36 visit, Analysis date of last dose)} - \text{Day 1 Date}) + 1) / 28}$$

Monthly is defined as a period of 4 weeks.

Subjects without a relevant concomitant medication record will be assumed that they used no IV iron, thus set to 0 mg.

The same method will be used to calculate monthly IV iron use for week 37-52 and 53-104. Analysis visits will be used as indicated in Section [7.11.4](#)

For subjects with use of IV iron, the time to first use of IV iron is calculated as:

$$(\text{First event date} - \text{Analysis date of first dose intake} + 1) / 365.25$$

With 'First event date' defined as 'Date of first IV iron' during the Efficacy Emergent Period and 'Analysis date of first dose intake' defined in Section [6.5.4](#)

For a subject without use of IV iron, the time to censoring is calculated as:

$$(\text{Date of End of Efficacy Emergent Period} - \text{Analysis date of first dose intake} + 1) / 365.25$$

With date of End of Efficacy Emergent Period defined in Section [7.11.6](#)

6.1.3.10 Occurrence and time to first use of ESA. Number of ESA-Weeks per year

The concomitant medication form of the eCRF in the cumulative visit will be used to detect rescue medication with ESAs as defined in Section [6.1.2.3](#)

The number of ESA-weeks per year are defined as the duration of ESA exposure divided by the total efficacy period in years. Each period when ESA [ATC code = B03XA] was taken will be summed by subjects as follows:

$$[\text{sum (each period (min(End date of efficacy emergent period, End date of ESA therapy) + X days} - \text{Start date of ESA therapy} + 1) / 7)] / \text{total period in years};$$

X will be defined as the duration of the effect of ESA following the last ESA administration, based on the following rules:

- If Frequency = 1 PER WEEK then X=7
- If Frequency = 2 PER WEEK then X=3
- If Frequency = 3 PER WEEK then X=2
- If Frequency = 1 PER MONTH then X=28
- If Frequency = ONCE then X=0
- If Frequency = BIM (Bi-monthly) then X=14
- If Frequency = QD (daily) then X=1

If Frequency = QM (monthly) then X=28
If Frequency = QOD (every other day) then X=2
If Frequency = TID (three times daily) then X=1
If Frequency = 4 TIMES PER WEEK then X=2
If Frequency = EVERY 3 WEEKS then X=21

Additional frequency may be considered depending on the data.

For subjects with use of ESA, the time to first use of ESA is calculated as:

$$(\text{First event date} - \text{Analysis date of first dose intake} + 1) / 365.25$$

With 'First event date' defined as 'Date of first ESA' and 'Analysis date of first dose intake' defined in Section [6.5.4](#)

For a subject without use of ESA, the time to censoring is calculated as:

$$(\text{Date of End of Efficacy Emergent Period} - \text{Analysis date of first dose intake} + 1) / 365.25$$

With date of End of Efficacy Emergent Period defined in Section [7.11.6](#)

6.1.3.11 Change from BL to each post-dosing study visit in Total cholesterol, LDL/High-density Lipoprotein (HDL) ratio, Non-HDL cholesterol, Apolipoproteins A1 and B, ApoB/ApoA1 ratio

For each sample the following will be calculated:

- LDL/HDL ratio (LDL Cholesterol divided by HDL Cholesterol)
- Non-HDL cholesterol (Total Cholesterol minus HDL Cholesterol)

Change from baseline to each post-dosing study visit will be calculated for the following lipid parameters:

- Total cholesterol
- LDL cholesterol
- HDL cholesterol
- Low-density lipoprotein (LDL) / high-density lipoprotein (HDL) ratio
- Non-HDL cholesterol
- Triglyceride
- Apolipoproteins A1 and B (ApoA1 and ApoB)
- ApoB/ApoA1 ratio.

All available data will be summarized descriptively for all parameters above, regardless of fasting status.

No imputation will be performed in case of a missing value. If several values are available in the same window, one value will be used, as defined in [Table 33](#) and Section [7.11.4](#)

Baseline assessment is the assessment from Day 1 visit. If this value is missing, then the latest screening period value will be used as baseline.

6.1.3.12 Occurrence of mean LDL cholesterol <100 mg/dL calculated over weeks 12 to 28

The evaluation period is defined as the average of all available LDL cholesterol values in weeks 12-28 (visit at 12, 20 and 28 weeks, as defined in [Table 33](#) and Section [7.11.4](#)). The occurrence of mean LDL cholesterol <100 mg/dL over weeks 12 to 28 will then be defined as a binary variable (Yes/No), where "Yes" is defined as mean LDL cholesterol <100 mg/dL over weeks 12 to 28.

No imputation will be performed in case of a missing value.

This endpoint will be reported on fasting values and regardless of fasting status.

6.1.3.13 Occurrence of achieved antihypertensive treatment goal in CKD subjects (SBP < 130 mmHg and DBP < 80 mmHg) based on the mean SBP and mean DBP calculated over weeks 12 to 28

Occurrence of achieved antihypertensive treatment goal (SBP < 130 mmHg and DBP < 80 mmHg) based on the mean SBP and mean DBP is calculated over an evaluation period defined as the average of all available values in weeks 12 to 28 during the Safety Emergent Period, similarly as in Section [6.1.2.6](#) (analysis windows defined in [Table 31](#) Section [7.11.4](#)). Occurrence of achieved antihypertensive treatment goal will then be defined as a binary variable (Yes/No), where "Yes" is defined as SBP < 130 mmHg and DBP < 80 mmHg.

No imputation will be performed in case of a missing value.

6.1.3.14 Change from BL to the average value of weeks 12 to 28 in Quality of Life scores

All study subjects will be required to complete Quality of Life (QoL) questionnaires as indicated in the schedule of assessments:

- SF-36
- FACT-An
- EQ-5D 5L
- WPAI:ANS

The next sections provide further details on how to derive these instruments, some derivations will be provided by an external vendor (QualityMetric).

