7.4.3.5 Categorical analysis for Hb values

Proportion of Hb values :

The proportion of Hb values within 10-12 g/dL or ≥ 10 g/dL is a quantitative variable in the 0 – 100 range for each subject. Descriptive statistics for this variable will be presented by treatment arm. This variable will be presented in weeks 28-36, in weeks 44-52 and in weeks 96 -104, on the FAS.

Percentage of time during the Efficacy Emergent Period:

Descriptive statistics for the percentage of time with Hb values falling in each interval interval (<10.0 g/dL, within 10.0-12.0 g/dL, > 12.0 g/dL, ≥ 10.0 g/dL, > 13.0 g/dL and > 14.0 g/dL) between the first and last Hb assesment during the Efficacy Emergent Period will be presented by treatment arm.

The number and percentage of subjects, and the number of events, will be reported based on Hb values from the central lab with Hb increase by >2.0 g/dL between any two visits within 4 weeks of treatment.

Time to first occurrence of potential EH will also be analyzed similarly as in Section [7.4.2.7](#) (except that all data during the Efficacy Emergent Period will be taken into account for the analysis). The results will be presented by period (First 6 weeks, Week 7 - Week 27, Week 28 - Week 52 and > Week 52)

7.4.3.6 Occurrence (number) of hospitalizations,number of days of hospitalization per PEY and time to first hospitalization

The number and percentage of subjects with hospitalization will be reported. Descriptive statistics and frequency tabulations by treatment arm of the total duration of hospitalization (days), the average duration of each hospitalization (days), the number of hospitalizations, number of days of hospitalization per PEY and reason for hospitalization will also be reported.

Time to first hospitalization will also be analyzed similarly as in Section [7.4.2.7](#) (except that all data during the Efficacy Emergent Period will be taken into account for the analysis).

Superiority will be declared if the upper bound of the two-sided 95% confidence interval of the hazard ratio of the two treatment arms is below 1. Both descriptive summary and time to first hospitalization will be reported by eGFR category (<15 vs ≥15).

As a sensitivity analysis, the above analysis will be repeated using IPCW method (Appendix 10.7).

The analysis will be done on the FAS.

7.4.3.7 Occurrence and time to first use of rescue therapy during the First 24 Weeks [composite of RBC transfusions, IV iron supplementation and rescue ESA]

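### SAP 6.1.3.5 defines the two visit dates in reverse in the Hb interpolation formula; coded literally, each boundary-crossing day is mirrored within its visit interval

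*SAP*

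**What the plan says.** Under the percentage-of-time part of SAP 6.1.3.5, each subject's time is divided among six Hb intervals: below 10.0, 10.0 to 12.0, at least 10.0, above 12.0, above 13.0 and above 14.0 g/dL. The method is named plainly: "The percentage of time will be calculated via linear interpolation". When the category changes between visits V0 and V1, the day of change is

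x = x0 + (y − y0)(x1 − x0)/(y1 − y0).

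The terms are then defined in one sentence. On the dates, named in the order x1 and then x0: they "are the dates when Hb was measured at V0 and V1 respectively". On the Hb values: "y_0 and y_1 are the Hb value at the respective visits V0 and V1". The level y is the Hb boundary, listed as 12.0, 13.0 or 14.0 g/dL. Time at or above 10 is obtained as 100% minus time below 10.

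The section then says what the result is for: "This calculation will provide the day that the change in Hb value occurs". Days in each category are counted from it and divided by the time between the first and last Hb assessment in the evaluated period. SAP 7.4.3.5 reports the outcome by arm over the Efficacy Emergent Period: "Descriptive statistics for the percentage of time with Hb values falling in each interval".

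**The concern.** The date subscripts run in the opposite direction to the Hb subscripts. The Hb values pair 0 with V0 and 1 with V1; the dates pair 1 with V0 and 0 with V1. Linear interpolation needs each date to carry the same subscript as the Hb measured on it.

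What is at stake is the summary of how long subjects spend in, below and above the 10.0 to 12.0 g/dL maintenance range, including time above 13 and 14. The SAP revision history says the measure was introduced to allow for differing treatment durations, and protocol 7.5 singles out excessive Hb response for attention among the laboratory data. A program that followed the definitions to the letter could misplace days within an interval, and could report more time above 13 than above 12, which is impossible.

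**Working it through.** The SAP gives no numerical result here, so there is no figure to reproduce. The check is algebra followed by examples.

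**Inputs.** The formula and definitions are from SAP 6.1.3.5. The 28-day spacing is the visit schedule after week 24 (SAP 3.2.3). The Hb values below are assumptions for illustration.

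**Algebra.** Let d0 and d1 be the dates of V0 and V1, L = d1 − d0, and f = (y − y0)/(y1 − y0).

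- Intended assignment (x0 = d0, x1 = d1): x = d0 + fL.
- Literal assignment (x0 = d1, x1 = d0): x = d1 − fL.
- The two sum to d0 + d1, so the literal day is the reflection of the intended day about the interval midpoint.
- Displacement (literal minus intended) = L(1 − 2f). It is zero at f = 0.5 and approaches L in size as the crossing nears either visit.

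**Endpoint check.** Put y equal to the Hb at V0, so f = 0. The intended assignment returns the V0 date; the literal one returns the V1 date.

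**Two boundaries crossed.** Hb 11.8 to 13.2, V0 = day 0, V1 = day 28.

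- 12.0 boundary: f = 0.2/1.4 = 1/7. Intended day 4; literal 28 − 4 = day 24.
- 13.0 boundary: f = 1.2/1.4 = 6/7. Intended day 24; literal 28 − 24 = day 4.
- Intended: 28 − 4 = 24 days above 12 and 28 − 24 = 4 days above 13.
- Literal: 28 − 24 = 4 days above 12 and 28 − 4 = 24 days above 13.

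**Direction and cancellation** (days above 12.0, each interval 28 days):

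| Hb at V0 to V1 | f | Intended | Literal | Error |
|---|---|---|---|---|
| 11.5 to 12.2 | 0.714 | 8 | 20 | +12 |
| 11.8 to 12.8 | 0.2 | 22.4 | 5.6 | −16.8 |
| 11.5 to 12.5 | 0.5 | 14 | 14 | 0 |
| 11.0 to 12.5 | 0.667 | 9.33 | 18.67 | +9.33 |
| 12.5 to 11.0 | 0.333 | 9.33 | 18.67 | +9.33 |
| 12.5 to 11.8 | 0.714 | 20 | 8 | −12 |

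- A rise from 11.0 to 12.5 followed by a fall back to 11.0 accumulates error: 9.33 + 9.33 = 18.67 days too many (unrounded values summed).
- The path 11.5, 12.2, 12.5, 11.8 cancels. The rise contributes +12 and the fall −12, and the middle interval lies wholly above 12. Both versions total 56 days (8 + 28 + 20, and 20 + 28 + 8).

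**One whole path.** Hb 9.0, 11.0, 12.5, 11.5, 11.2, 12.2, 11.6 at 28-day visits, 168 days in all.

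- Intended time above 12: 9.33 + 14 + 5.6 + 9.33 = 38.27 days, or 22.8%.
- Literal: 18.67 + 14 + 22.4 + 18.67 = 73.73 days, or 43.9%.

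**The case against.** The strongest reply is that this is a slip in a definition, not a wrong method. The formula is the standard one, the section names linear interpolation, and it points to Figure 1 as a picture of the calculation. The literal reading contradicts all of that, since it places the Hb measured at V0 on the V1 date. A programmer who recognises linear interpolation would probably code it correctly, and SAP section 1 plans a review of data and outputs before hard lock. This stands, and it makes wrong output a risk rather than a certainty. It does not rescue the sentence: it assigns the dates explicitly, and no other part of the SAP text corrects it. Figure 1 was not available in the copy examined, so nothing is claimed about it.

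The consequence is also limited. SAP 7.4.3.5 asks only for descriptive statistics on percentage of time, outside the testing sequence in SAP Table 16. Overshoot and control are also covered by measures that do not use this formula: potential excessive hematopoiesis, time to Hb above 14 g/dL, the proportion of values in range, and categories of averaged Hb. This stands too.

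A reader might infer that the missing 10.0 boundary leaves three intervals undefined. The documents do not support that: the below-10.0 and 10.0 to 12.0 intervals are named, and time at or above 10 is derived from time below 10. The omission is one of completeness.

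**Conclusion.** The date definitions in SAP 6.1.3.5 are reversed relative to the Hb definitions. Followed literally, they reflect each crossing day about the midpoint of its interval, moving it by L(1 − 2f). With 28-day visits the displacement ranges from zero to just under 28 days for a single crossing. Time above a boundary can be overstated or understated. The algebra rests only on the SAP's definitions; the worked day counts rest on assumed Hb values.

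Three stronger readings do not follow:

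- **That reported times are wrong.** The documents show what the SAP instructs, not what was programmed.
- **That every subject who crosses a boundary is affected.** Midpoint crossings are unchanged, and a subject's errors can net to zero.
- **That errors on a rise and a later fall cannot cancel.** They add for a symmetric rise and fall, but the path 11.5, 12.2, 12.5, 11.8 cancels exactly.

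No primary or key secondary analysis uses the calculation. The point is a correctable error in an operative rule for a descriptive output.

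**What to change.** In SAP 6.1.3.5, define x0 as the date of the V0 measurement and x1 as the date of the V1 measurement, leaving the formula and the Hb definitions as they are. List the boundary levels as 10.0, 12.0, 13.0 and 14.0 g/dL.

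Then confirm that the program uses the corrected assignment. The simplest test is the endpoint check: a boundary set equal to the Hb at V0 must return the V0 date. Checking that time above 12 is at least time above 13, and that at least time above 14, is a useful extra but weaker, because a mirrored interval that crosses only one boundary need not break that order.

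The cost is one line of wording, one addition to a list and a short program check. No new data are needed. If the outputs have already been produced from the literal definitions, only the percentage-of-time tables need rerunning.
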